Subsequently, in June 2021, as a result of a signal evaluation procedure (EPITT number 19382) to assess the increased incidence rate of major adverse cardiovascular events (MACE) and malignancies excluding non-melanoma skin cancer (NMSC) in patients treated with tofacitinib for RA, the European Medicines Agency (EMA) concluded that myocardial infarction (MI), lung cancer, and lymphoma were important identified risks. To minimise these risks, and the important potential risk of MACE and malignancies excluding NMSC, the EMA recommended that the SmPC be updated to include restrictions on use of tofacitinib in patients over 65 years of age, patients who are current or past smokers, patients with other CV risk factors, and patients with other malignancy risk factors (e.g., current malignancy or history of malignancy other than a successfully treated NMSC). In these patients, tofacitinib should only be used if no suitable treatment alternatives are available.

In conjunction with the initial authorisation in March 2017, to minimise important potential and identified risks associated with the use of tofacitinib and to continue to monitor important potential and identified risks, the Marketing Authorisation Holder (MAH) implemented an educational program designed to increase awareness of the risks of tofacitinib in each member state of the European Union (EU). This program consists of routine (i.e., SmPC and patient package insert) and additional risk minimisation measures (aRMMs; i.e., a prescriber brochure, checklists for treatment initiation and treatment maintenance, and a patient alert card to distribute to patients). There is also a website where healthcare professionals (HCPs) can access the aRMM materials.

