Serious and opportunistic infections of interest (including HIV, HZ, TB, and viral hepatitis B and	Comorbidity	Defined as $\geq 1$ ICD-10 diagnosis code for a serious and/or opportunistic infection of interest.
C)		DIAGNOSIS CODES FOR SELECT INFECTIONS OF INTEREST.
Diverticulitis	Comorbidity	Defined as ≥1 ICD-10 diagnosis code for diverticulitis.

 Table 3.
 Operational definitions of study variables in the selected databases

° The data sources are unable to reliably ascertain severity of hepatic impairment and renal impairment.

<sup>p The data sources may not be able to differentiate between active and latent TB.

Variable	Role	Operational definition
Malignancy (non- metastatic and metastatic, excluding non-melanoma skin cancer)	Comorbidity	Defined as ≥1 ICD-10 diagnosis code for a malignancy (excluding non-melanoma skin cancer).
Non-melanoma skin cancer	Comorbidity	Defined as ≥1 ICD-10 diagnosis code for non-melanoma skin cancer.
Gastrointestinal perforation	Comorbidity	Defined as $\geq 1$ ICD-10 diagnosis code for gastrointestinal perforation.
Interstitial lung disease	Comorbidity	Defined as ≥1 ICD-10 diagnosis code for interstitial lung disease.
		Complete list in ANNEX 4. LIST OF DIAGNOSIS AND PROCEDURE CODES FOR INTERSTITIAL LUNG DISEASE.
Diabetes	Comorbidity	Defined as ≥1 ICD-10 diagnosis code for diabetes.
Immunodeficiencies of interest	Comorbidity	Defined as $\geq$ 1 ICD-10 diagnosis code for immunodeficiency.
		Complete list in ANNEX 5. LIST OF DIAGNOSIS CODES FOR SELECT IMMUNODEFICIENCIES OF INTEREST.
Prior use of corticosteroids	Medication history	Defined as ≥1 prescription dispensing of a corticosteroid (as identified by ATC code[s]) in the 12 months prior to the index tofacitinib dispensing.
		Complete list in ANNEX 7. LIST OF ATC CODES FOR COMEDICATIONS OF INTEREST.
Prior use of statins	Medication history	Defined as $\geq 1$ prescription dispensing of a statin (as identified by ATC code[s]) in the 12 months prior to the index tofacitinib dispensing.
		Complete list in ANNEX 7. LIST OF ATC CODES FOR COMEDICATIONS OF INTEREST.

 Table 3.
 Operational definitions of study variables in the selected databases

Variable	Role	Operational definition
Prior use of any biologic q	Medication history	Defined as ≥1 prescription dispensing of a biologic (as identified by ATC code[s]) in the 12 months prior to the index tofacitinib dispensing.

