Chronic kidney disease	Outcome: CV risk factor	Defined as ≥1 ICD-10 diagnosis code for chronic kidney disease while receiving tofacitinib.
Stable angina pectoris	Outcome: CV risk factor	Defined as ≥1 ICD-10 diagnosis code for stable angina pectoris while receiving tofacitinib.
Discontinuation of tofacitinib after developing ≥1 CV risk factors while taking tofacitinib	Outcome: CV risk factor	Defined as ≥1 CV risk factor while receiving tofacitinib therapy (as listed and defined above) PLUS 0 prescription dispensings for tofacitinib within a specific time window after the code for the CV risk factor.
		Note: The time window for when to look for a tofacitinib prescription dispensing will be specific to the CV risk factor acquired while receiving tofacitinib therapy and will be operationalized during SAP development.
		Duration of tofacitinib therapy defined in Section 9.3.3.
Continuation of tofacitinib after developing ≥1 CV risk factors while taking tofacitinib	Outcome: CV risk factor	Defined as $\geq 1$ CV risk factor while receiving tofacitinib therapy (as listed and defined above) PLUS $\geq 1$ prescription dispensing for tofacitinib within a specific time window after the code for the CV risk factor.
		Note: The time window for when to look for a tofacitinib prescription dispensing will be specific to the CV risk factor acquired while receiving tofacitinib therapy and will be operationalized during SAP development.
		Duration of tofacitinib therapy defined in Section 9.3.3.

 Table 3.
 Operational definitions of study variables in the selected databases

Variable	Role	Operational definition	
Analysis of malignancy ris	Analysis of malignancy risk factors in patients using tofacitinib y		
Assessment of malignancy re	Assessment of malignancy risk factors prior to initiation of tofacitinib		
Elderly at tofacitinib initiation (patients 65 years and older)	Outcome: Malignancy risk factor	Calculated as the date of tofacitinib initiation minus the patient's year of birth and reported in the following categories: $<65$ years and $\geq 65$ years.	
History of malignancy (non-metastatic and metastatic, excluding non- melanoma skin cancer)	Outcome: Malignancy risk factor	Defined as ≥1 ICD-10 diagnosis code for a malignancy (excluding non-melanoma skin cancer) in the 12 months prior to or on the day of the index tofacitinib dispensing.	

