Current or past smoker x	Outcome: Malignancy risk factor	Defined as $\geq 1$ ICD-10 diagnosis code for tobacco use disorder or $\geq 1$ procedure code for counselling visits for smoking or $\geq 1$ prescription dispensing (as identified by ATC code[s]) for a nicotine replacement product in the 12 months prior to or on the day of the index tofacitinib dispensing.	
Initiating tofacitinib with ≥1 malignancy risk factor	Outcome: Malignancy risk factor	Defined as ≥1 malignancy risk factor (as listed and defined above) identified in the 12 months prior to or on the day of the index tofacitinib dispensing.	
Initiating tofacitinib with ≥1 malignancy risk factor and no prior use of an alternative therapy (i.e., biologic)	Outcome: Malignancy risk factor	Defined as ≥1 malignancy risk factor (as listed and defined above) identified in the 12 months prior to or on the day of the index tofacitinib dispensing—AND— 0 prescription medication dispensings for a biologic (as identified by ATC code) in the 12 months prior to and including the date of the index tofacitinib prescription dispensing.	
		Complete list of biologics in ANNEX 6. LIST OF ATC CODES FOR MEDICATIONS OF INTEREST TO AVOID WHILE TAKING TOFACITINIB	
Assessment of malignancy risk factors while receiving tofacitinib therapy (duration of tofacitinib therapy defined in Section 9.3.3)			

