# Table 3. Operational definitions of study variables in the selected databases

Elderly (patients 65 years	Outcome: Malignancy risk factor	Defined as patients aged 65 years or
and older)		older while receiving tofacitinib.

<sup>y In GKV claims, outpatient diagnoses are reported quarterly.

Variable	Role	Operational definition
Malignancy (non- metastatic and metastatic, excluding non-melanoma skin cancer)	Outcome: Malignancy risk factor	Defined as ≥1 ICD-10 diagnosis code for a malignancy (excluding non-melanoma skin cancer) while receiving tofacitinib.
Current smoker x	Outcome: Malignancy risk factor	Defined as $\geq 1$ ICD-10 diagnosis code for tobacco use disorder or $\geq 1$ procedure code for counselling visits for smoking or $\geq 1$ prescription dispensing (as identified by ATC code[s]) for a nicotine replacement product while receiving tofacitinib.
Discontinuation of tofacitinib after developing ≥1 malignancy risk factors while taking tofacitinib	Outcome: Malignancy risk factor	Defined as ≥1 malignancy risk factor while receiving tofacitinib therapy (as listed and defined above) PLUS 0 prescription dispensings for tofacitinib within a specific time window after the code for the malignancy risk factor. Note: The time window for when to look for a tofacitinib prescription dispensing will be specific to the malignancy risk factor acquired while receiving tofacitinib therapy and will be operationalized during SAP development. Duration of tofacitinib therapy defined in Section 9.3.3.
Continuation of tofacitinib after developing ≥1 malignancy risk factors while taking tofacitinib	Outcome: Malignancy risk factor	Defined as ≥1 malignancy risk factor while receiving tofacitinib therapy (as listed and defined above) PLUS ≥1 prescription dispensing for tofacitinib within a specific time window after the code for the malignancy risk factor. Note: The time window for when to look for a tofacitinib prescription dispensing will be specific to the malignancy risk factor acquired while receiving tofacitinib therapy and will be operationalized during SAP development. Duration of tofacitinib therapy defined in Section 0.3.2
		Section 9.3.3.

 Table 3.
 Operational definitions of study variables in the selected databases

Variable	Role	Operational definition	
Compliance to recommendations for limitations of contraindicated use z			

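### Table 3 removes every non-melanoma skin cancer from the malignancy risk factor, although the restriction being evaluated exempts only a successfully treated one

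*Protocol*

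**What the plan says.** Section 7 (Rationale and Background) describes the restrictions that followed the 2021 signal evaluation. Besides older patients, smokers and patients with other cardiovascular risk factors, they cover "patients with other malignancy risk factors (e.g., current malignancy or history of malignancy other than a successfully treated NMSC". The consequence follows: "In these patients, tofacitinib should only be used if no suitable treatment alternatives are available".

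Section 9.3.2, Table 3, turns this into variables. The baseline malignancy item is "Defined as ≥1 ICD-10 diagnosis code for a malignancy (excluding non-melanoma skin cancer) in the 12 months prior to or on"; its window closes on the index date. The on-treatment item is "Defined as ≥1 ICD-10 diagnosis code for a malignancy (excluding non-melanoma skin cancer) while receiving tofacitinib". The baseline composite is "Defined as ≥1 malignancy risk factor (as listed and defined above) identified in the 12 months prior to or on the day of" index, and a second version adds the absence of a prior biologic. Two further outcomes count patients who stop or continue tofacitinib after acquiring a malignancy risk factor on treatment.

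Sections 9.7.1.2.2.1.4 and 9.7.1.3.4 tabulate these overall, by individual factor and by CV and Malignancy Reporting Period. They list three factors: elderly, malignancy and smoking. NMSC appears separately in Table 3 as a comorbidity, "Defined as ≥1 ICD-10 diagnosis code for non-melanoma skin cancer", and does not feed any malignancy risk-factor outcome.

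**The concern.** Primary Objective 2 asks whether prescribers follow the limitations of use, so the risk-factor variable should identify the patients to whom the limitation applies. Section 7 uses two different ideas. The safety risk is malignancies excluding NMSC. The restricted patient group is anyone with current or past malignancy, less those whose NMSC was successfully treated. Table 3 appears to carry the exclusion from the first idea into the second.

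A patient who starts tofacitinib with an active NMSC, or who is first diagnosed with one on treatment, is inside the restriction as Section 7 words it, yet the malignancy item records nothing. The item feeds an individually reported row, two baseline composites and two on-treatment outcomes, so the omission recurs in each. Section 9.9 discusses malignancies missed beyond 12 months and the weak capture of smoking, but does not mention this gap.

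**Working it through.** This is a question of definition, so the main check sets the texts side by side.

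- **NMSC, successfully treated before index.** Section 7: exempt. Table 3 baseline item: not counted. They agree.
- **NMSC, current or not yet successfully treated at index.** Section 7: restricted. Table 3 baseline item: not counted. They disagree.
- **First NMSC diagnosed on treatment.** Section 7: restricted, since treatment cannot already have succeeded when it is first diagnosed. Table 3 on-treatment item: not counted. They disagree.
- **Any other malignancy coded in the window.** Section 7: restricted. Table 3: counted. They agree.

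Every disagreement runs the same way: the count of restricted patients can only be too low.

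Next, how far the omission reaches:

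1. *Individual malignancy row.* Every patient whose only malignancy is a current NMSC is missing.
2. *Composites of one or more factors.* The composite is the union of age 65 or older, malignancy and smoking. A patient with NMSC is missing only if under 65 and not flagged as a smoker. The smoking flag is a weak safeguard: a footnote to Table 3 warns of possible very low sensitivity and says it will be reported only if feasible.
3. *Stopping or continuing after a new factor.* An on-treatment NMSC code does not trigger these outcomes. A patient may still enter through age or smoking, but the observation window then follows that factor and not the NMSC code.

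Size for the composite. The undercount, as a share of all initiators, is

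undercount = q × s,

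where q is the share of initiators with a current NMSC and s is the share of those who are under 65 and not flagged as smokers. The protocol gives neither. Both ranges below are assumptions:

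- q = 0.5%, s = 20%: 0.005 × 0.20 = 0.001, or 0.1 percentage points
- q = 1%, s = 40%: 0.01 × 0.40 = 0.004, or 0.4 percentage points
- q = 2%, s = 60%: 0.02 × 0.60 = 0.012, or 1.2 percentage points
- q = 3%, s = 60%: 0.03 × 0.60 = 0.018, or 1.8 percentage points

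For scale, the precision target in Section 9.5 is a 95% interval of total width 20 points at a proportion of 50%: 0.50 × 0.50 × 1.96² / 0.10² = 96.04, so 97 patients, rounded up to 100. That figure reproduces and is not affected by this point.

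**The case against.** The strongest reply is that Section 7 is a background summary with an illustrative parenthesis. Compliance is judged against the risk minimisation materials, which are not in the protocol, and Section 7 describes their aim in terms of malignancies excluding NMSC. Section 9.3.2 also calls its algorithms preliminary. This stands in part: the wording of the materials cannot be checked here. But Section 7 is the protocol's own statement of the restriction, and its parenthesis exempts only successfully treated NMSC. The exclusion is not a code-list detail either. It is written into the variable names and definitions, and Section 9.7 says that major changes to primary endpoint definitions go through an amendment.

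A second reply is that codes may not separate current from treated NMSC, so excluding all of it protects specificity. The difficulty is real. A rule that looks for a treatment procedure after the diagnosis would not work in the German claims, where outpatient diagnoses carry only a quarter (Sections 9.4.4 and 9.9), and a procedure does not prove success. That argues for showing both versions, not for an unstated exclusion.

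Third, NMSC is not lost. Section 9.7.1.1 tabulates it before and after index and by age, so the number of patients under 65 with an NMSC code will be visible. What remains missing is the split by reporting period and prior biologic, and the link to stopping or continuing.

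A reader might also infer that every patient with current NMSC is scored as free of malignancy risk factors, or that non-compliance is understated in every reporting period. The documents support neither. Patients aged 65 or older, or flagged as smokers, still count in the composite. CV and Malignancy Reporting Period 1 ends on 30 June 2021, before the notification and the revised materials that define the later periods (Section 9.2.2). Having a risk factor is not itself non-compliance, because use is allowed when no suitable alternative exists.

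**Conclusion.** The definition in Table 3 does not match the restriction in Section 7. The individual malignancy row omits current and not yet successfully treated NMSC. The composites omit the subset under 65 and not flagged as smokers, and new on-treatment NMSC does not enter the stopping and continuing outcomes through the malignancy item. The direction is certain: the restricted group is undercounted.

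The size is not known, because the documents give no NMSC frequency. For the composite it is probably small, 0.1 to 1.8 percentage points on the assumed values. The individual row and the on-treatment outcomes are affected more directly, but no figure for them can be supported. A ratio of assumed NMSC to assumed other malignancy would look precise, yet it would rest on invented rates and count exempt patients as missed. Because the same definition applies in all periods, the effect on the before-and-after description should be smaller than on the level. The mismatch itself is certain and the correction is cheap, so it should be made.

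**What to change.** In Table 3 and in Sections 9.7.1.2.2.1.4 and 9.7.1.3.4, report each of the following twice: the individual malignancy row; the composites of one or more malignancy risk factors, both regardless of prior biologic use and without a prior biologic; and the discontinuation and continuation outcomes. One version excludes NMSC, as now, and is the lower bound. The other adds the NMSC codes already defined as a comorbidity and is the upper bound; label it as containing some exempt, successfully treated patients. The bounds apply to the count of patients with a coded factor in the study window. Where the denominator is patients who acquired a factor, the proportion who stop or continue may move either way and should be shown simply as two versions.

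Add to Section 9.9 that diagnosis codes may not separate current from successfully treated NMSC, and that the version without NMSC errs downward. No procedure-based rule is needed.

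The cost is a few extra table rows and one limitation sentence. There is no new data extraction and no change to the sample size.

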# Table 3. Operational definitions of study variables in the selected databases

Elderly (patients 65 years	Outcome: Malignancy risk factor	Defined as patients aged 65 years or
and older)		older while receiving tofacitinib.

<sup>y In GKV claims, outpatient diagnoses are reported quarterly.

Variable	Role	Operational definition
Malignancy (non- metastatic and metastatic, excluding non-melanoma skin cancer)	Outcome: Malignancy risk factor	Defined as ≥1 ICD-10 diagnosis code for a malignancy (excluding non-melanoma skin cancer) while receiving tofacitinib.
Current smoker x	Outcome: Malignancy risk factor	Defined as $\geq 1$ ICD-10 diagnosis code for tobacco use disorder or $\geq 1$ procedure code for counselling visits for smoking or $\geq 1$ prescription dispensing (as identified by ATC code[s]) for a nicotine replacement product while receiving tofacitinib.
Discontinuation of tofacitinib after developing ≥1 malignancy risk factors while taking tofacitinib	Outcome: Malignancy risk factor	Defined as ≥1 malignancy risk factor while receiving tofacitinib therapy (as listed and defined above) PLUS 0 prescription dispensings for tofacitinib within a specific time window after the code for the malignancy risk factor. Note: The time window for when to look for a tofacitinib prescription dispensing will be specific to the malignancy risk factor acquired while receiving tofacitinib therapy and will be operationalized during SAP development. Duration of tofacitinib therapy defined in Section 9.3.3.
Continuation of tofacitinib after developing ≥1 malignancy risk factors while taking tofacitinib	Outcome: Malignancy risk factor	Defined as ≥1 malignancy risk factor while receiving tofacitinib therapy (as listed and defined above) PLUS ≥1 prescription dispensing for tofacitinib within a specific time window after the code for the malignancy risk factor. Note: The time window for when to look for a tofacitinib prescription dispensing will be specific to the malignancy risk factor acquired while receiving tofacitinib therapy and will be operationalized during SAP development. Duration of tofacitinib therapy defined in Section 0.3.2
		Section 9.3.3.

 Table 3.
 Operational definitions of study variables in the selected databases

Variable	Role	Operational definition	
Compliance to recommendations for limitations of contraindicated use z			
Initiating tofacitinib with severe hepatic impairment aa	Outcome: Contraindicated use	Defined as ≥1 ICD-10 diagnosis code for severe hepatic impairment in the 12 months prior to and including the day of tofacitinib initiation.	
Initiating tofacitinib while pregnant	Outcome: Contraindicated use	Defined as tofacitinib initiation (i.e., the index date) occurring between the beginning and end of a pregnancy, as identified in the Swedish MBR and in the Perinatal Registry of the PHARMO Database Network (Netherlands) ; or as estimated using a combination of pregnancy-related diagnosis and/or procedure codes in the Swedish NPR, in NHIFA, the Hungarian administrative claims database, and in GKV claims (Germany).	
Receiving tofacitinib while pregnant	Outcome: Contraindicated use	Defined as evidence of a pregnancy while receiving tofacitinib therapy in the follow-up period, as identified in the Swedish MBR and in the Perinatal Registry of the PHARMO Database Network (Netherlands); or as estimated using a combination of pregnancy-related diagnosis and/or procedure codes in the Swedish NPR, in NHIFA, the Hungarian administrative claims database, and in GKV claims (Germany). Duration of tofacitinib therapy defined in Section 9.3.3.	
Initiating tofacitinib while having TB (active or latent) bb	Outcome: Contraindicated use	Defined as ≥1 ICD-10 diagnosis code for TB in the 60 days prior to and including the day of tofacitinib initiation.	
Initiating tofacitinib while having a serious and/or opportunistic infection	Outcome: Contraindicated use	
 
Defined as ≥1 ICD-10 diagnosis code for a serious and/or opportunistic infection in the 60 days prior to and including the day of tofacitinib initiation.
 
Complete list of serious and/or opportunistic infections in ANNEX 3.
 
LIST OF DIAGNOSIS CODES FOR SELECT INFECTIONS OF INTEREST.
 
	

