### 9.2.3. Patient-specific study period

Patients will be included in the study analyses if they have  $\geq 1$  tofacitinib prescription dispensing during the indexing period and meet the study inclusion and exclusion criteria (described in Section 9.2.4 [Inclusion criteria] and 9.2.5 [Exclusion criteria], respectively). The date of a patient's first tofacitinib prescription dispensing during the indexing period will be considered the patient's **index date**. Each patient will have their own unique **study period** (based on their index date), consisting of a 12-month **baseline period** and a 12-month **follow-up period** (Figure 4).

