### 9.3.2. Variable definitions

Table 3 summarises and defines the study variables to be collected and analysed in the selected databases. Unless otherwise specified, these variables will be assessed during each patient's entire study period, baseline period, and follow-up period.

This study will use code-based algorithms from the literature (validated against a gold standard measure, where possible) and/or other code lists to identify study variables. All code-based algorithms and code lists will be reviewed and/or approved by the study sponsor

prior to study initiation. Preliminary algorithms and/or codes are proposed in the following table (see also ANNEX 3 through ANNEX 7). Final algorithms and/or code lists will be refined as part of the SAP development.

Where possible, operational definitions for the variables listed in Table 3 will be similar across the databases. Only ICD-10 diagnosis codes and procedure codes are referenced in Table 3; the specific coding systems used in each data source will be further described in the SAP. See Section 9.4 (Data sources) for a description of the selected databases and Section 9.9 (Limitations of the research methods) for a summary of the limitations associated with these databases.

Variable	Role	Operational definition		
Indication m				
Indication n	Indication (including potential off-label indications)	Reported in the following categories: RA, PsA, UC, and Other / unknown (i.e., potential off-label indications).		
		Defined as $\geq 1$ International Classification of Disease, 10 th Revision (ICD-10) diagnosis code for RA, PsA, or UC in the 12 months prior to and including the day of tofacitinib initiation. If there is no ICD-10 diagnosis code in the patient's data for RA, PsA, or UC during this time period, then the indication will be reported as Other / unknown. If a patient has multiple codes for any combination of indications (e.g., RA and PsA), the ICD-10 diagnosis code closest to the index tofacitinib prescription dispensing will be used to determine indication.		
Primary Objective 1: Demo	Primary Objective 1: Demographics, comorbidities, and prior and current medications m			

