The PDR, maintained by the National Board of Health and Welfare, contains all prescribed and dispensed medication for patients in Sweden. Coverage of prescriptions is close to 100%, however, inpatient administrations are not captured and there is only partial capture of drugs administered in hospital outpatient visits. Information included in the PDR include basic demographic characteristics such as age, sex, and residency, as well as medication-specific information such as the prescribed / dispensed drug (e.g., ATC code, International Non-proprietary Names [INN]), prescription dispensing date, pack size, dispensed amount, formulation, dosage, prescribing healthcare practitioner, and costs. The PDR is updated monthly. The Swedish MBR was established in 1973 and is managed by the National Board of Health and Welfare (NBHW). The register covers 100% of births and stillbirths of at least 22 gestational weeks since July 2008 (and of at least 28 gestational weeks before July 2008) in Sweden thereby facilitating the identification of tofacitinib exposure during pregnancy. There are no data on elective terminations or spontaneous abortions in the register. The register covers information such as gestational duration, self-reported smoking status during pregnancy, diagnoses during pregnancy, date of birth, delivery complications, diagnoses of the mother and the child, Apgar score, low birthweight, head circumference and survival. The data for the previous calendar year are usually available in December of the following year. Access to the register data for scientific research is decided by the NBHW through a standard application procedure and is assessed on a case-by-case basis.

The NCR was started in 1958 and is managed by the NBHW. The registry records all newly diagnosed tumours and blood cancers diagnosed by clinical, morphological, or other laboratory examinations, as well as cases diagnosed at autopsy. Since the mid-1980s, there are six regional registries associated with the oncological centres in each medical region of Sweden where the registration, coding, and major check-up and correction work is performed. The register includes information on patient characteristics, tumour characteristics, diagnosis, and date and cause of death. Data are updated on an annual basis with a lag time of approximately 13 months. Applications for data access are sent to the National Board of Health and Welfare and processed by a pre-defined data permit process.

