### 9.7. Data analysis

Detailed methodology for summary and statistical analyses of data collected in this study will be documented in a SAP, which will be dated, filed, and maintained by the sponsor. The SAP may modify the plans outlined in the protocol; any major modifications of primary endpoint definitions or their analyses would be reflected in a protocol amendment. Interim study report 1 will cover data from 01 April 2016 through 31 December 2020. Interim study report 2 will cover data from 01 April 2016 through 31 December 2022. The final study report will cover data from 01 April 2016 through 31 December 2024. If it is necessary to extend the study observation period for a country because the *minimum* number of tofacitinib patients (100 patients) per indication has not been met for all three indications by the end of the study observation period, the study observation period will be extended for those countries as the data are available.

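### Receipt of tofacitinib in pregnancy is read partly (Sweden) or solely (Netherlands) from birth or perinatal registers, with no stated look-forward for births after the 12-month follow-up and data that end with the last follow-up

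*Protocol*

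**What the plan says.** Table 3 of the protocol (Section 9.3.2) defines the outcome as "Defined as evidence of a pregnancy while receiving tofacitinib therapy in the follow-up period, as identified in the Swedish MBR". The Dutch source named there is the PHARMO network's perinatal registry. Alternatively, pregnancy is estimated from diagnosis and procedure codes in the Swedish NPR, the Hungarian NHIFA and the German GKV claims. No code route is named for the Netherlands. The neighbouring row, on initiating while pregnant, asks for "tofacitinib initiation (i.e., the index date) occurring between the beginning and end of a pregnancy".

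For rows that specify nothing else, Section 9.3.2 says that "these variables will be assessed during each patient's entire study period, baseline period, and follow-up period". Section 9.2.3 describes the patient's study period as "consisting of a 12-month baseline period and a 12-month" follow-up, and uses that follow-up to ascertain contraindicated use after initiation.

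On the Swedish Medical Birth Register, Section 9.4.1 says: "The register covers 100% of births and stillbirths of at least 22 gestational weeks since July 2008", and: "There are no data on elective terminations or spontaneous abortions in the register". It also lists gestational duration among the variables held. Section 9.4.3 says that the Dutch registry holds data on pregnancies, births and neonatal outcomes, including gestational age.

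Section 9.7 sets the data end: "The final study report will cover data from 01 April 2016 through 31 December 2024". Under Section 9.2.1 the last index date is 31 December 2023, so the last follow-up also ends on 31 December 2024.

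**The concern.** A register built on births reveals a pregnancy only at its end. A pregnancy that starts late in a 12-month follow-up ends after it. The woman then counts in the denominator, while her pregnancy can reach the numerator only if a later birth record is read and dated back. The protocol does not say that this will be done, and for late initiators the data stop before such a record could exist.

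Receipt in pregnancy is one of the contraindicated-use measures. Any loss of this kind lowers the numerator and leaves the denominator alone, so the reported proportion errs towards no contraindicated use. Section 9.9 lists no limitation on the capture of pregnancies.

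**Working it through.** **Figures the protocol gives.** It states no figure for pregnancy capture. Its calendar reproduces: April 2016 to December 2024 is 8 x 12 + 9 = 105 months of observation, and April 2017 to December 2023 is 6 x 12 + 9 = 81 months of indexing.

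**Inputs.** Follow-up F = 365 days (Section 9.2.3); data end 31 December 2024 (Section 9.7). The remaining inputs are assumptions, since the documents do not give them:
- gestation g = 266 to 280 days
- pregnancy starts spread evenly over time on therapy
- time on therapy T = 90, 180 or 365 days
- index dates spread evenly over the indexing period.

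**Reading A: births read only within follow-up.** A pregnancy is seen if it starts by day F - g, so the share seen is min(T, F - g)/T. F - g is 365 - 280 = 85 days or 365 - 266 = 99 days.

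| Time on therapy | Seen, g = 280 | Seen, g = 266 | Missed |
|---|---|---|---|
| 365 days | 85/365 = 23.3% | 99/365 = 27.1% | 73-77% |
| 180 days | 85/180 = 47.2% | 99/180 = 55.0% | 45-53% |
| 90 days | 85/90 = 94.4% | all | 0-6% |

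**Reading B: births read to the data end and dated back.** Only women indexed in the last year lose anything. With T = 365, onset is the sum of two uniform one-year times. Because 2024 is a leap year, the latest onset falls one day before the data end. The share missed is therefore ((g - 1)/365)^2 / 2:
- g = 280: (279/365)^2 / 2 = 0.292
- g = 266: (265/365)^2 / 2 = 0.264

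Over the whole indexing period this is 0.292 x 12/81 = 4.3% and 0.264 x 12/81 = 3.9%. A simulation gave 29.2% and 26.3% for last-year initiators, 4.3% and 3.9% overall, and zero for earlier initiators. With 180 days of therapy it gave 4.9-6.7% for last-year initiators and 0.7-1.0% overall.

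**Interim reports under reading B (T = 365).** Report 1 covers data to December 2020, so the last index date with full follow-up falls in December 2019 and the index span is 33 months. The loss is 0.264 x 12/33 = 9.6% to 0.292 x 12/33 = 10.6%. Report 2 covers data to December 2022, with an index span of 57 months, and loses about 0.29 x 12/57 = 6%. Swedish annual patient counts rose from 336 to 889 to 1912 in 2017-2019 (Table 7). If initiations rose likewise, even uptake understates the share at report 1.

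**Pregnancy already under way at index.** It ends within about 280 days of index, inside the 365-day follow-up. Such pregnancies are not lost, and the row on initiating while pregnant works under either reading.

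**The case against.** The strongest reply is that the definition requires the pregnancy, not the delivery, to fall in follow-up. Both registers hold gestational duration or age, so a later birth can be dated back. The data are retrospective extracts. On that reading the overall loss is about 4% or less. This stands: the protocol nowhere requires the birth record to be dated inside follow-up, so reading A is one possible reading of an unclear rule.

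A reader might infer that most on-treatment pregnancies in the study go unrecorded. The documents do not support that, for four reasons:
- The figure of about three quarters needs both reading A and 12 months of persistence.
- Hungary and Germany use codes, which do not wait for a birth record.
- Sweden adds NPR codes, though the NPR omits GP encounters (Section 9.4.1).
- Recording only at delivery is not stated for the Dutch registry.

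The Dutch numbers are also small: 280 patients of both sexes through 2019 (Table 9).

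It can also be said that the search window belongs in the analysis plan, which is not shown. Section 9.3.2 does defer final algorithms and code lists. But the tie to follow-up, the named sources and the data end are set in the protocol, and the data end limits late initiators however the algorithm is refined.

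The neighbouring row may seem to imply reading beyond follow-up. It does not, because a pregnancy under way at index ends inside follow-up.

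**Conclusion.** The point holds as a gap in the outcome definition and a cut-off loss that depends on the data end. In the birth-register sources, whether births after follow-up count is unstated. If they do not, up to about three quarters of pregnancies starting on treatment are missed in the register, depending on persistence. If they are read to the data end, about 26-29% are still missed for last-year initiators: about 4% overall at the final report, 10-11% at interim report 1 and about 6% at interim report 2, all with 12 months on therapy. The sizes rest on even onset, even uptake and a gestation of 266-280 days. The direction does not: the error is always towards no contraindicated use.

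The Netherlands is most exposed, since its registry is the only source named, provided that registry records at birth. Sweden is exposed to the extent that NPR codes miss the same pregnancies. Separately, terminations, miscarriages and stillbirths before 22 weeks are absent from the Swedish birth register whatever the window.

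**What to change.** 1. State in Table 3 that birth-register records dated after follow-up are read up to the data cut-off, and that each pregnancy is dated back using gestational duration.
2. For this outcome in the birth-register sources, leave out of the denominator, or report separately, women whose follow-up ends less than about 42 weeks before the data cut-off. Apply this at each interim report and at the final report. Waiting for later births is not workable for the last Swedish initiators: births in 2025 would usually reach the register in December 2026 (Section 9.4.1), after the planned end of data collection on 31 October 2026 (Section 6).
3. For the Netherlands, add pregnancy-related codes from the PHARMO hospital and GP databases for linked patients. Report them separately, because linkage is partial: Table 9 puts the GP overlap at 30%, or 0.30 x 280 = 84 of the patients counted through 2019.
4. List missing terminations and early losses as a limitation in Section 9.9.

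The cost is a few sentences, a smaller denominator for this one outcome and a little more analysis work.
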